11.5. Serum Pharmacokinetic Parameters

The individual serum concentration versus actual time data for mRNA-2416 and durvalumab will be used to derive the PK parameters using non-compartmental PK analyses with Phoenix WinNonlin version 8.0 or higher.

The following serum PK parameters will be calculated for mRNA-2416 and durvalumab if data permit:

C_{\max}	Maximum observed serum concentration, obtained directly from the observed concentration time data.
t_{\max}	Time to maximum observed serum concentration, obtained directly from the observed concentration time data.
AUC_{0-t}	AUC from 0 hour to the time of the last observed quantifiable serum concentration (C_{last}); calculated by linear up log down trapezoidal method.
$AUC_{0-\infty}$	AUC extrapolated to infinity; calculated as $[AUC_{0-t} + (C_{\text{last}}/\lambda_z)]$
%AUC	Percentage of estimated part of the calculation of $AUC_{0-\infty}$, calculated as: $((AUC_{0-\infty} - AUC_{0-t}) / AUC_{0-\infty}) \times 100$; If %AUC extrapolated is higher than 30%, then $AUC_{0-\infty}$ and parameters derived from it will be displayed in the listing (flagged) and excluded from descriptive statistics and statistical analysis.
λ_z	Apparent elimination rate constant, estimated by linear regression of the terminal portion of the log-concentration by time curve; a minimum of 3 non-BLQ data points in the elimination phase (not including C_{\max}) will be used for the calculation. The λ_z will not be estimated if adjusted r-squared is less than 0.8.
$t_{1/2}$	Apparent elimination half-life, calculated as $[(\ln 2)/\lambda_z]$. If the length of the time interval used to determine λ_z is less than 2 times $t_{1/2}$, then $t_{1/2}$ will be flagged (i.e., $t_{1/2}$ values that are more than half the time interval used to determine λ_z will be flagged).

Adjusted r-squared, number of points to calculate slope of terminal phase and start and end of the λ_z will be listed. Additional parameters may be calculated if deemed necessary.

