10.13 BIOMARKERS

In this study, biomarker samples will be collected per Tables 6, 7,8 and 9. The biomarker analysis will be used to investigate the effect of mRNA-2416, as well as to determine how the markers are associated with clinical outcome. Immune responses will be studied in the peripheral circulation and in tumor biopsy specimens. Tumor biopsies will be examined using methods such as immunohistochemistry, quantitative immunofluorescence, RNA sequencing and/or electrochemiluminescence (ECL) assays to evaluate changes in key immune pathway axes, such as PD-L1/PD-1 and OX40L/OX40, as well as characterization (eg, phenotype, distribution, and activation) of tumor infiltrating lymphocyte and myeloid populations. Cytokines may also be examined in both tumor and blood tissues using methods such as RNA sequencing and enzyme-linked immunosorbent assay (ELISA)/ ECL assays, respectively.

The goal of the biomarker assessments is to provide supportive data for the clinical study; however, there may be circumstances when a decision is made to stop a collection or not perform or discontinue an assessment (eg, inadequate sample number, sample quality or assay issues that preclude analysis, or impossibility to perform correlative analyses). Therefore, sample collection and/or assessment may be omitted at the discretion of the Sponsor.

The sample collection information must be entered on the appropriate sample collection log eCRF page(s). Sample details including volume and instructions for the collection, handling, and shipment of samples are outlined in the laboratory manual for the study.

Table 6: Sampling schedule for Pharmacokinetics, Immunogenicity, and Cytokine Profiling

Cycle	Day	Scheduled Time (Sampling Window)	Purpose ^a
1	1	Pre-dose of Cycle 1 Day 1	PK, Cytokines, IG
1	1	3 h from start of injection (\pm 10 min)	PK, Cytokines
1	1	6 h from start of injection (\pm 30 min)	PK, Cytokines
1	2	24 h from start of injection (\pm 60 min)	PK, Cytokines
1	8	168 h from start of injection (\pm 24 h)	PK, Cytokines
1	15	Pre-dose of Cycle 1 Day 15	IG
2	1	Pre-dose of Cycle 2 Day 1	PK, Cytokines, IG, mAb PK
3	1	Pre-dose of Cycle 3 Day 1	IG
3	15	Pre-dose of Cycle 3 Day 15	IG
4	1	Pre-dose of Cycle 4 Day 1	IG
5	1	Pre-dose of Cycle 5 Day 1	IG
6	1	Pre-dose of Cycle 6 Day 1	IG
6	15	Pre-dose of C1D15	IG
EOT		Anytime	IG
Unscheduled		Anytime when needed	PK, Cytokines, IG, mAb PK

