3.3. Treatment

Two investigational products, mRNA-2416 and durvalumab, are tested on patients with advanced relapsed/refractory solid tumor malignancies or lymphoma. mRNA-2416 is a novel mRNA encoding human OX40L encapsulated in a lipid nanoparticle, administered through repeated intratumoral injections on tumor lesions. Durvalumab in combination with mRNA-2416 in arm B is administered to study patients through intravenous infusion.

Arm A patients receiving treatment to superficial lesions will receive mRNA-2416 on Day 1 and Day 15 of a 28-day cycle for 6 cycles. Arm A patients receiving treatment to visceral lesions and all Arm B patients will receive mRNA-2416 on Day 1 and Day 15 for Cycle 1, and on Day 1 only for Cycles 2-6. All Arm B patients will receive durvalumab in combination with mRNA-2416 on Day 1 in each cycle. Dose levels of mRNA-2416 can be found in the protocol Table 1 and Table 2. In the event that ≥ 2 of the first 6 DLT-evaluable patients in the 8.0 mg cohort experience a DLT, an intermediate dose cohort may be opened at 6.0 mg mRNA-2416. Per protocol, the potential dose cohorts are 0.5 mg, 1.0 mg, 2.0 mg, 4.0

mg, 6.0 mg, and 8.0 mg of mRNA-2416 alone, and 2.0 mg, 4.0 mg, 6.0 mg, and 8.0 mg of mRNA-2416 in combination with durvalumab. Some cohorts may not have any patients enrolled during the course of the study. Only the dose cohorts that have patients enrolled will be analyzed. If the dose level of mRNA-2416 that a patient received at the first dose is different from the dose cohort that the patient was enrolled in, the patient may be analyzed in the dose level of mRNA-2416 that the patient received as specified in the analysis.

Following are the potential treatment arms and dose cohorts for Phase I and Phase II.

- Arm A
 - mRNA-2416 0.5 mg
 - mRNA-2416 1.0 mg
 - mRNA-2416 2.0 mg
 - mRNA-2416 4.0 mg
 - mRNA-2416 6.0 mg
 - mRNA-2416 8.0 mg
- Arm B
 - mRNA-2416 2.0 mg + Durvalumab
 - mRNA-2416 4.0 mg + Durvalumab
 - mRNA-2416 6.0 mg + Durvalumab
 - mRNA-2416 8.0 mg + Durvalumab

4. General Statistical Considerations

This document will provide details regarding the definition of analysis variables and analysis methodology to address all study objectives.

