4.3.4. PK Analysis Set

The PK analysis set is a subset of the safety set for patients who have at least one baseline and post-baseline serum PK concentration result. Patients with protocol deviations, or who experience dosing or other issues which are deemed to affect the PK data, will be considered for exclusion from the PK analysis set on a case-by-case basis. Patients will be included in the dose cohort corresponding to the dose level which they actually received.

5. Patient Disposition

Patient disposition data will be summarized using the safety set by treatment arm and dose cohort of mRNA-2416 (as specified in [Section 3.3](#)), total for each treatment arm combining Phase I and Phase II, and overall of Arm A and Arm B, unless otherwise specified.

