11.2. Values Below the Limit of Quantitation or Missing

Concentration values that are below the limit of quantification (BLQ) will be set to zero, with defined exceptions as follows:

- Any embedded BLQ value (between 2 quantifiable concentrations) and BLQ values following the last quantifiable concentration in a profile will be set to missing for the purposes of PK analysis.
- If there are late positive concentration values following 2 BLQ concentration values in the apparent terminal phase, these values will be evaluated. If these values are considered to be anomalous, they will be set to missing.
- If an entire concentration-time profile is BLQ, the profile will be excluded from the PK analysis.
- If a pre-dose concentration is missing, these values may be set to zero.

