11.4. Serum Concentration

Blood samples for determination of mRNA-2416 serum concentrations and durvalumab serum concentrations will be collected via venipuncture or an indwelling catheter in Cycle 1 at pre-dose (prior study drug administration), at 3, 6 and 24 (Cycle 1 Day 2) hours post-dose and at pre-dose on Cycle 1 Day 8 and Cycle 2 Day 1.

Serum concentration data of mRNA-2416 and durvalumab will be individually listed and summarized using descriptive statistics by nominal time point (n, mean, standard deviation, coefficient of variation [CV], geometric mean, median, minimum, and maximum). Geometric mean will not be calculated where the minimal concentration values include zero.

Geometric mean serum concentration by nominal time profiles by period and treatment both in linear and semi-logarithmic scale will be provided; individual serum concentration plots by actual sampling time for all patients combined within period and treatment will be provided on a linear and semi-logarithmic scale.

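### mRNA-2416 half-life and AUC0-inf are obtainable only in patients who peak at 3 h and are still quantifiable at 168 h, and AUC0-t can stop at 24 h or 168 h, so cohort comparisons need a pre-specified common-window AUC

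*SAP*

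**What the plan says.** **Sampling.** SAP 11.4 places the samples after the first pre-dose draw "at 3, 6 and 24 (Cycle 1 Day 2) hours post-dose and at pre-dose on Cycle 1 Day 8 and Cycle 2 Day 1". Protocol Table 6 (section 10.13) agrees: the first post-dose sample is "3 h from start of injection", and the Day 8 sample is "168 h from start of injection", with a window of 24 h either side. The last scheduled mRNA-2416 sample is "Pre-dose of Cycle 2 Day 1". SAP 3.3 doses visceral-lesion Arm A patients and all of Arm B "on Day 1 and Day 15 for Cycle 1, and on Day 1 only for Cycles 2-6"; superficial-lesion Arm A patients also receive Day 15 of Cycle 1.

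**Derivation.** SAP 11.5 estimates lambda-z from "a minimum of 3 non-BLQ data points in the elimination phase", Cmax excluded, and only with an adjusted r-squared of at least 0.8. AUC0-inf leaves the summaries when more than 30% of it is extrapolated. AUC0-t runs to the patient's own last quantifiable sample, and SAP 11.2 turns BLQ values after that sample into missing.

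**Reporting.** SAP 11.1 analyses PK by arm and dose cohort, and 11.6 summarises every parameter descriptively. Cmax and AUC are secondary endpoints (protocol 7.4, SAP 3.2.2). No AUC over a common window is specified.

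**PK set.** SAP 4.3.4 admits patients with "at least one baseline and post-baseline serum PK concentration result". SAP 11.2 adds: "If a pre-dose concentration is missing, these values may be set to zero".

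**The concern.** The estimability rule and the sampling times fit together poorly. With four samples before the second dose and three needed after the peak, the parameters that depend on lambda-z can come from only one kind of profile. The 144 h gap between the last two samples also means that AUC0-t does not end gradually earlier or later: it tends to end at 24 h or at 168 h. Which of these applies depends partly on dose, through the ratio of concentration to assay limit. Two dose cohorts, or two arms, could then show different AUC0-t or half-life summaries because different patients and different intervals contribute, without any difference in kinetics.

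The PK set raises a smaller issue. A patient whose Cycle 1 Day 1 pre-dose sample is missing fails 4.3.4, although 11.2 would allow that very value to be taken as zero.

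**Working it through.** The plan gives no expected number of estimable profiles, so there is no figure of its own to reproduce.

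**1. Which profiles meet the 3-point rule (documents only).** The peak can fall at 3, 6, 24 or 168 h, and the last quantifiable sample at or after it: 4 + 3 + 2 + 1 = 10 patterns. The most points available after the peak are:

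| Peak at | Later samples | Maximum points |
|---|---|---|
| 3 h | 6, 24, 168 h | 3 |
| 6 h | 24, 168 h | 2 |
| 24 h | 168 h | 1 |
| 168 h | none | 0 |

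Only one pattern in ten qualifies. Cycle 2 Day 1 does not help: it is about 672 h after dose 1 but about 336 h after the Day 15 dose. The SAP does not say that it is excluded.

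**2. Half-life needed to be quantifiable at 168 h.** For mono-exponential decline from 3 h, the requirement is half-life ≥ (168 − 3)/log2(C3/LLOQ), where C3 is the 3 h concentration:

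- C3/LLOQ 10: 165/3.32 = 49.7 h
- 100: 165/6.64 = 24.8 h
- 1000: 165/9.97 = 16.6 h
- 10000: 165/13.29 = 12.4 h

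The threshold moves with dose. There is also an upper limit for AUC0-inf: more than 30% is extrapolated once 2^(−168/half-life) exceeds 0.3, which is a half-life above 168/1.737 = 97 h.

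**3. Effect on AUC0-t across doses.** Assumptions: half-life 18 h, first-order input at 2 per h, C3/LLOQ 200 at 1 mg, concentrations proportional to dose, linear-up log-down trapezoids. C3/C168 = 2^(165/18) = 575, so C168/LLOQ is 200/575 = 0.35 at 1 mg, then 0.70, 1.39 and 2.78 at 2, 4 and 8 mg. AUC0-t therefore ends at 24 h for the two lower doses and at 168 h for the two higher ones. Per mg (initial-concentration scale 1):

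- 0 to 3, 3 to 6 and 6 to 24 h: 1.36 + 2.57 + 10.51 = 14.44
- 24 to 168 h: 10.47, giving 24.90 in total

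The ratio is 24.90/14.44 = 1.72, under exactly linear kinetics. True AUC is 18/ln 2 = 25.97, so AUC0-t captures 56% at the lower doses and 96% at the higher ones. AUC0-24h is 14.44 per mg at all four doses.

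**4. Who is estimable (simulation).** 4000 one-compartment profiles per scenario under the SAP rules. Median half-life, input rate (ka), C3/LLOQ and the spread between patients are all assumptions. Selected scenarios:

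| Median half-life | C3/LLOQ | ka per h | Estimable | Median true half-life, estimable vs all | AUC0-t ends at 168 h |
|---|---|---|---|---|---|
| 12 h | 100 | 0.5 | 3% | 25.8 vs 12.0 h | 10% |
| 12 h | 100 | 2 | 5% | 27.8 vs 11.9 h | 9% |
| 24 h | 100 | 2 | 25% | 33.5 vs 24.1 h | 47% |
| 24 h | 10000 | 2 | 52% | 24.0 vs 23.5 h | 89% |
| 48 h | 1000 | 2 | 48% | 45.5 vs 47.5 h | 98% |
| 48 h | 10000 | 0.5 | 23% | 42.3 vs 47.5 h | 100% |

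At long half-lives the selection reverses slightly, because slow eliminators tend to peak later and lose the third point.

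**5. Is the qualifying pattern sufficient?** Not always. Concentrations of 100, 50, 5 and 1 at 3, 6, 24 and 168 h have the right pattern, but the three post-peak points give an adjusted r-squared of 0.50, below the 0.8 limit.

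**The case against.** A reader might infer that only slow eliminators yield a half-life, so that half-life will be overstated and the exposure summaries cannot be compared at all. The documents do not support that. The gate is an early peak plus quantifiability at 168 h. A slow eliminator who peaks at 6 h is lost, and the 30% rule drops the slowest from AUC0-inf summaries. With no LLOQ and no half-life in the documents, the direction of any bias is unknown. If everyone is quantifiable at 168 h, AUC0-t has a common end and that part of the problem disappears. Cmax needs neither lambda-z nor a last quantifiable time, and SAP 11.4 summarises concentrations at common nominal times. All of this stands.

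The SAP also has safeguards. Parameters are derived only when the data allow, n is displayed, the number of points and the fit are listed, doubtful half-lives are flagged, and further parameters may be added. PK is descriptive, with no formal dose-proportionality or between-arm test. Cohorts can exceed 3 to 6: protocol 8.2.2 allows up to 9 biopsy patients per cleared Arm A dose level, and 13.2 plans about 30 and 45 expansion patients. These points lower the stakes. They show that profiles were lost, but they neither secure a comparable AUC nor tell the reader that AUC0-t ended at different times.

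On the PK set, the conflict is narrow: 11.2 is permissive, and because 11.4 calls Cycle 1 Day 8 and Cycle 2 Day 1 pre-dose as well, its rule is not confined to baseline. For a missing Cycle 1 Day 1 value, the two sections still point in opposite directions.

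**Conclusion.** The structural point holds without assumptions: one profile pattern in ten can give lambda-z, half-life and AUC0-inf, and AUC0-t has no common end time unless all patients are quantifiable at the same last sample. These summaries may therefore describe a selected subset, and AUC0-t comparisons across doses or arms can be distorted.

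The size is conditional. Over assumed median half-lives of 12 to 48 h and C3/LLOQ of 100 to 10000, 3% to 52% of profiles are estimable. Selection is strong towards slow elimination at short half-lives and low ratios, and negligible or slightly reversed at long half-lives or high ratios. The 1.72-fold AUC0-t artefact is one example in which the assumed half-life lies between the thresholds of adjacent doses; it is not a prediction. The issue affects a descriptive secondary endpoint and leaves Cmax untouched. It is a minor point, worth correcting because the correction is cheap.

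**What to change.** In SAP 11.5:

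- Add AUC0-24h (pre-dose, 3, 6 and 24 h) as the pre-specified AUC for comparing dose cohorts and arms. Give it an explicit rule for a BLQ 24 h value, for example zero for this parameter only. Otherwise 11.2 makes that value missing and fast eliminators drop out again.
- Keep AUC0-t, AUC0-inf and half-life as planned. Protocol 13.4.4 calls for descriptive statistics where possible, so removing those summaries would depart from it. Beside them, show the number and percentage estimable per cohort and the distribution of the last quantifiable time.
- State that Cycle 2 Day 1 is not used for the first-dose lambda-z.

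In SAP 4.3.4, require only at least one post-dose result, and set a missing Cycle 1 Day 1 pre-dose value to zero, with the wording of 11.2 aligned to match.

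The cost is SAP wording, one extra derived parameter and two added display items, with no new samples. The limitation is that AUC0-24h captures only part of total exposure when elimination is slow: at a 48 h half-life about 1 − 2^(−24/48) = 29%. It should therefore supplement the other AUCs and not replace them.

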11.6. Statistical Analysis of Pharmacokinetic Parameters

Pharmacokinetic parameters derived from serum concentrations will be individually listed and summarized. The PK parameters with the exception of t_{\max} will display n, mean, standard deviation, CV, geometric mean, median, minimum, and maximum as descriptive statics. However, t_{\max} will only display n, median, minimum and maximum.

For the listings, concentration data will be presented to the same precision as the data is received. All PK parameters will be presented in the listings to 3 significant figures with the exception of t_{\max} , which will be presented to 2 decimal places.

For summary statistics, the following precisions should be used:

- n should be presented to zero decimal places
- CV% should be presented to 1 decimal place
- Mean, standard deviation, geometric mean, median, minimum, and maximum should be presented to the same precision as the listings

12. Interim Analysis

No formal interim analysis is planned.

13. Changes in the Planned Analysis

One of the exploratory endpoints, assessment of the correlation of other investigational serum-based proteins (e.g., anti-drug antibodies) with PK, efficacy, and safety, is not included in this statistical analysis plan.

14. References

Eisenhauer EA et al. New response criteria in solid tumours: revised RECIST guideline (version 1.1). *Eur J of Cancer.* 2009; 45(2):228-247.

DocuSign Envelope ID: B20D66AA-D718-4BD5-9F79-8CFF4FE948CA

Statistical Analysis Plan (SAP) Client Approval Form

Client:	ModernaTX, Inc.
Protocol Number:	mRNA-2416-p101
Document Description:	Final Statistical Analysis Plan
SAP Title:	A Phase I/II, Open-label, Multicenter, Dose Escalation and Efficacy Study of mRNA-2416, a Lipid Nanoparticle Encapsulated mRNA Encoding Human OX40L, for Intratumoral Injection Alone and in Combination with Durvalumab for Patients with Advanced Malignancies
SAP Version Number:	1.0
Effective Date:	29NOV2021
Author(s):	
For PPD: PPD	
For Moderna: PPD	
Approved by:	
PPD	Date (DD-MMM-YYYY)
Biostatistics and programming, PPD	
PPD	Date (DD-MMM-YYYY)
Clinical Development, Moderna, Inc.	
PPD	Date (DD-MMM-YYYY)
Biostatistics, Moderna, Inc.
